Fecal sample collection n	X o			X	X	X	X		X	X		

g Full physical examinations will be performed at the Screening, ETT, and Safety Follow-up Visits; abbreviated physical examinations will be performed at all other study visits.

h Vital signs and ECGs will be taken predose through the Week 24 Visit. Following the Week 24 Visit, vital signs and ECGs may be taken pre- or post-dose. Vital signs include blood pressure (systolic and diastolic), temperature, heart rate, respiratory rate, and pulse oximetry (see Section 11.6.3).

i All 12-lead ECGs will be performed predose at the Day 1, Week 12 and Week 24 Clinic Visits. At all visits, ECGs will be taken before any other procedures that may affect heart rate, such as blood draws (see Section 11.6.4).

j To minimize blood draws, the Screening Visit and Day 1 clinical laboratory assessments can be combined into a single blood draw taken up to 9 days before the Day 1 dosing. The results must be received and reviewed before the first dose of study drug.

k The OE will be conducted by a licensed ophthalmologist, preferably a pediatric ophthalmologist. The OE may be performed at the study visit or ± 14 days of the clinic visit.

l If an OE was conducted in Study 124 Part A within 12 weeks of the Day 1 Visit, the Day 1 Visit OE does not need to be repeated.

m The OE for the ETT Visit will be conducted for all subjects who prematurely discontinue ivacaftor dosing in the ivacaftor arm, regardless of the reason for discontinuation. If the ETT Visit occurs within 12 weeks of the subject's last OE, the OE at the ETT Visit will not be required.

**Table 3-3 Schedule of Assessments for VX15-770-126 (Ivacaftor Arm: Study 124 Part A Only Subjects or Subjects Not From Study 124)**

Event/Assessment	Screening Period a	Treatment Period (Day 1 through Week 96)								ETT Visit b	Safety Follow-up Visit c	24-Week Follow-up OE
	Day -28 to Day -1	Day 1	Day 3 (± 1 Day)	Week 2 (± 1 Day)	Week 4 (± 5 Days)	Weeks 8 and 18 (± 7 Days)	Weeks 12 and 24 (± 7 Days)	Weeks 36, 60, and 84 (± 7 Days)	Weeks 48, 72, and 96 (± 7 Days)	As Soon as Possible After the Last Dose	4 Weeks (± 7 Days) After the Last Dose	24 Weeks (+ 14 Days) After the Last Dose
Sweat chloride test p	X	X		X			X		X			
Qualitative microbiology cultures		X					X		X			
Multiple breath washout (optional) q		X					X		X r			

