##### **12.3.4.1 Adverse Events**

TEAEs, defined as adverse events with start date or increased severity on or after the first dose of ivacaftor through the end of participation (as applicable) in this study, will be summarized by treatment. TEAEs will hereafter be referred to as adverse events. Adverse event summary tables will include the following analyses presented by treatment:

- All adverse events
- Related (defined as possibly related or related) adverse events
- Adverse events leading to treatment discontinuation

- SAEs
- Adverse events by severity
- Adverse events by relationship

Summaries will be presented by MedDRA system organ class and preferred term using frequency counts and percentages. A subject with multiple occurrences of the same adverse event or a continuing adverse event will be counted only once, with the highest severity or relationship.

In addition, a table containing individual subject adverse event data for all deaths and other serious and significant adverse events will be provided.

**Pretreatment AEs** are defined as AEs that were reported or worsened after signing the ICF up to the start of study drug dosing.

**Treatment-emergent AEs** are defined as AEs that were reported or worsened on or after the start of study drug dosing through the the end of participation (as applicable) in this study.

Only TEAEs will be summarized in tables. All summaries of TEAEs will be presented by the severity of the AE and relationship to the study drug. Some rules that will apply to the summarization of AEs are as follows: (1) a subject with multiple occurrences of the same AE or a continuing AE will only be counted once; (2) only the maximum severity level will be presented in the severity summary; and (3) only the worst relationship level will be presented in the relationship summary.

AEs leading to death, SAEs, dose interruption, and permanent discontinuation will be listed separately. All AEs through the Safety Follow-up Visit will be listed in an individual subject data listing, including pretreatment AEs.

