8 STATISTICAL ANALYSIS

8.1 General Considerations

The Schedule of Assessments is provided in [Appendix A](#). The precision standards for reporting safety and efficacy variables are provided in an internal Biometrics document that specifies the programming rules including the precision for derived variables.

All individual subject data for subjects who are enrolled in the current study will be presented in individual subject data listings.

As no subjects are enrolled in the Observation Arm, all analyses will be done for subjects from the Ivacaftor Arm only. All analysis will be performed for the Ivacaftor Arm overall, unless otherwise specified.

Continuous variables will be summarized using the following descriptive summary statistics: the number of subjects (n), mean, standard deviation (SD), standard error (SE), median, minimum value (min), and maximum value (max). 95% confidence intervals (CI) may be provided as appropriate.

Categorical variables will be summarized using counts and percentages. 95% CI may be provided as appropriate.

Baseline value is defined in two different ways:

Study 124 baseline: the baseline value for rollover subjects (who participated in Study 124 Part B or Part A/B) is defined as the baseline measurement from Study 124 Part B or Part A/B. That is, the most recent non-missing measurement collected on or before the initial

administration of study drug in Study 124 Part B or Part A/B. Note that this definition is consistent with the definition of baseline in Study 124 and applies to both scheduled and unscheduled measurements; if an unscheduled value is the most recent non-missing measurement, it will be used as baseline.

Study 126 baseline: the baseline value for IVA-naïve subjects (who did not participate in Study 124 Part B or Part A/B) is defined as the most recent non-missing measurement collected on or before the initial administration of study drug in the current study, including both the scheduled and unscheduled measurements.

Change (absolute change) from baseline will be calculated as Postbaseline value – Baseline value.

Relative change from baseline will be calculated and expressed in percentage as 100% × (Postbaseline value – Baseline value)/Baseline value.

Treatment-emergent (TE) Period

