For the Ivacaftor Arm, the TE period will include the time period starting from the first dose date of the study drug in the current study to the Safety Follow-up Visit, or the last dose date + 28 days for subjects who do not have a Safety Follow-up Visit. The TE period will be used for safety analyses unless specified otherwise.

Unscheduled visits: Unscheduled visit measurements will be included in analysis as follows:

- In scheduled visit windows per specified visit windowing rules
- In the derivation of baseline/last on-treatment measurements.
- In the derivation of maximum/minimum on-treatment values and maximum/minimum change from baseline values for safety analyses.
- In individual subject data listings as appropriate.

Visit windowing rules: The analysis visit windows for protocol-defined visits in the Ivacaftor Arm are provided in Appendix B. The windows will be applied using the following rules for both scheduled and unscheduled visits. If no measurement is available within a visit window, the assessment will be considered missing for the visit. If there is more than one measurement available within the same visit window, the following rules will be used:

- For all safety parameters, if there are multiple measurements within a visit window, then 1) the record closest to the target day will be used, with the exception of the threshold analysis in which the worst record will be used; 2) if there are multiple records within the same distance of the target day, the latest record will be used; or 3) the Safety Follow-Up (SFU) visit will not be windowed; instead, the nominal visit will be used in relevant analyses.
- For all efficacy parameters, if there are multiple measurements within a visit window, the record at the scheduled visit will be used. Otherwise,
 - If there are no measurements at the scheduled visit, then the record closest to the target day will be used;

- If there are multiple records with the same distance to the target day, the latest record will be used.
- Assessments at the early treatment termination (ETT) visit will follow the windowing rules for regular visits, with the exception of the ETT visit occurs 21 days or later after the last dose, which will be treated as SFU visit.

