8.4.3 Electrocardiogram

For treatment-emergent ECG measurements, a summary of raw values and change from baseline values will be provided by visit for the following standard 12-lead ECG measurements: RR (ms), HR (bpm), PR (ms), QRS duration (ms), QRS axis (degrees), QT (ms), and QT corrected for HR intervals [QTcF (ms)].

The number and percentage of subjects meeting at least 1 threshold analysis criterion during the TE period for the Treatment Period will be summarized. The threshold analysis criteria are provided in Appendix E.

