⁴⁰ Length and weight measurements will be performed predose through the Week 24 Visit (see CSP Section 11.5.1).

⁴¹ Full physical examinations will be performed at the Screening, ETT, and Safety Follow-up Visits; abbreviated physical examinations will be performed at all other study visits.

⁴² Vital signs and ECGs will be taken predose through the Week 24 Visit. Following the Week 24 Visit, vital signs and ECGs may be taken pre- or post-dose. Vital signs include blood pressure (systolic and diastolic), temperature, heart rate, respiratory rate, and pulse oximetry (see CSP Section 11.6.3).

⁴³ All 12-lead ECGs will be performed predose at the Day 1, Week 12 and Week 24 Clinic Visits. At all visits, ECGs will be taken before any other procedures that may affect heart rate, such as blood draws (see CSP Section 11.6.4).

⁴⁴ To minimize blood draws, the Screening Visit and Day 1 clinical laboratory assessments can be combined into a single blood draw taken up to 9 days before the Day 1 dosing. The results must be received and reviewed before the first dose of study drug.

Table 11-3 Schedule of Assessments for VX15-770-126 (Ivacaftor Arm: Study 124 Part A Only Subjects or Subjects Not From Study 124)

Event/Assessment	Screening Period ³⁵	Treatment Period (Day 1 through Week 96)								ETT Visit ³⁶	Safety Follow-up Visit ³⁷	24-Week Follow-up OE
	Day -28 to Day -1	Day 1	Day 3 (± 1 Day)	Week 2 (± 1 Day)	Week 4 (± 5 Days)	Weeks 8 and 18 (± 7 Days)	Weeks 12 and 24 (± 7 Days)	Weeks 36, 60, and 84 (± 7 Days)	Weeks 48, 72, and 96 (± 7 Days)	As Soon as Possible After the Last Dose	4 Weeks (± 7 Days) After the Last Dose	24 Weeks (+ 14 Days) After the Last Dose
Ophthalmologic examination ⁴⁵	X ⁴⁶						X		X	X ⁴⁷		X
Fecal sample collection ⁴⁸	X ⁴⁹			X	X	X	X		X	X		
Sweat chloride test ⁵⁰	X	X		X			X		X			
Qualitative microbiology cultures		X					X		X			

⁴⁵ The OE will be conducted by a licensed ophthalmologist, preferably a pediatric ophthalmologist. The OE may be performed at the study visit or ± 14 days of the clinic visit.

⁴⁶ If an OE was conducted in Study 124 Part A within 12 weeks of the Day 1 Visit, the Day 1 Visit OE does not need to be repeated.

⁴⁷ The OE for the ETT Visit will be conducted for all subjects who prematurely discontinue ivacaftor dosing in the ivacaftor arm, regardless of the reason for discontinuation. If the ETT Visit occurs within 12 weeks of the subject's last OE, the OE at the ETT Visit will not be required.

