⁵¹ MBW will be performed on subjects for whom additional or separate informed consent was obtained for the procedures, and only at sites that are adequately trained and qualified to perform this assessment (CSP Section 11.5.6). The Day 1 MBW must be performed within 1 week before the first dose, not postdose. The Week 96 MBW must be performed within 1 week before the last dose, not after the last dose. Detailed procedures will be supplied in a separate study manual.

⁵² MBW will be performed at the Week 48 and Week 72 Visits (± 7 days).

⁵³ The morning dose of study drug will be administered at the Day 1, and 2-, 4-, 8-, 12-, 18-, and 24-Week Clinic Visits. After the Week 24 Visit, the morning dose need not be administered at the Clinic Visit. Additional guidance for preparation and administration of study drug is provided in CSP Section 9.4 and the study manual.

Table 11-3 Schedule of Assessments for VX15-770-126 (Ivacaftor Arm: Study 124 Part A Only Subjects or Subjects Not From Study 124)

Event/Assessment	Screening Period ³⁵	Treatment Period (Day 1 through Week 96)								ETT Visit ³⁶	Safety Follow-up Visit ³⁷	24-Week Follow-up OE
	Day -28 to Day -1	Day 1	Day 3 (± 1 Day)	Week 2 (± 1 Day)	Week 4 (± 5 Days)	Weeks 8 and 18 (± 7 Days)	Weeks 12 and 24 (± 7 Days)	Weeks 36, 60, and 84 (± 7 Days)	Weeks 48, 72, and 96 (± 7 Days)	As Soon as Possible After the Last Dose	4 Weeks (± 7 Days) After the Last Dose	24 Weeks (+ 14 Days) After the Last Dose
Adverse events	Continuous from signing ICF through the Safety Follow-up Visit (see CSP Section 13.1.1.3)										Ocular adverse events only	
Medications and procedures review	Continuous from signing of ICF through the Safety Follow-up Visit											

CF: cystic fibrosis; *CFTR*: CF transmembrane conductance regulator gene; ETT: Early Termination of Treatment; ICF: informed consent form; MBW: multiple breath washout; LFT: liver function test; OE: ophthalmologic examination; q12h: every 12 hours.

Appendix B: Analysis Visit Windows for Safety and Efficacy Assessments**Table 11-4 Analysis Visit Windows for Safety and Efficacy Assessments - Rollover Subjects From Study 124 Part B or Part A/B**

Assessment	Visit ^a	Target Study Day	Analysis Visit Window (in study days)
Safety Assessments			
Serum Chemistry Hematology Vital Signs	Baseline	Not applicable	parent study baseline
	Week 12	84	[2, 126]
	Week 24	168	[127, 210]
	Week 36	252	[211, 294]
	Week 48	336	[295, 378]
	Week 60	420	[379, 462]

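### Read literally, SAP 8.1 lets a Day 1 predose ECG or lab value count as a child's worst treatment-emergent value in the QTcF and LFT threshold tables

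*SAP*

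**What the plan says.** SAP 8.1 has the TE period "starting from the first dose date of the study drug in the current study" and ends it at the Safety Follow-up Visit, or 28 days after the last dose if there is no such visit. It adds: "The TE period will be used for safety analyses unless specified otherwise".

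The ECG threshold table in SAP 8.4.3 reports "The number and percentage of subjects meeting at least 1 threshold analysis criterion during the TE period". SAP 8.4.2 uses the same period for the selected LFT parameters. The visit-window rules in SAP 8.1 say that threshold analysis takes the worst record.

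On Day 1 timing, Protocol Table 3-3, footnote i, states: "All 12-lead ECGs will be performed predose at the Day 1, Week 12 and Week 24 Clinic Visits". The schedules in SAP Appendix A repeat it: "Vital signs and ECGs will be taken predose through the Week 24 Visit". Under Protocol 9.1.1.1, screening labs more than 9 days old are repeated on Day 1 and reviewed before the first dose.

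For IVA-naive children, SAP 8.1 sets the baseline as the "most recent non-missing measurement collected on or before the initial administration of study drug in the current study". For rollovers, SAP Appendix B, Table 11-4, uses the "parent study baseline".

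**The concern.** The TE period is set by calendar date, but the Day 1 assessments come before the dose on that date. A record made before the first Study 126 dose therefore meets the definition of treatment-emergent. In a table built on each child's worst record, it can decide which category the child falls in.

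Safety is the primary endpoint (Protocol 7.1.1), and the study is open-label and descriptive, with about 75 children. One child placed in a QTcF or transaminase band by a record that predates Study 126 dosing would be a visible change in a small table. Any error runs upward, since adding a record to a maximum can raise it but never lower it.

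**Working it through.** The plan gives no figure to reproduce on this point. The check traces the Day 1 record through the rules, then sizes the effect.

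**1. Where the Day 1 ECG goes**

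| Group | What the Day 1 ECG is | SAP baseline | Appendix B window | In TE period by date |
|---|---|---|---|---|
| IVA-naive | Before the first Study 126 dose | Study 126; can be this record | Baseline (day 1 or earlier) | Yes |
| Gap Transition | Off drug; how long depends on the gap | Study 124 | None | Yes |
| Same-day Transition | On-drug Study 124 Week 24 record | Study 124 | None | Yes |

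A Day 1 lab draw, where one was taken, follows the same path.

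**2. Which outputs it can reach**

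- By-visit summaries: not reached. The first postbaseline windows all open on day 2, for example ECG [2, 56] for IVA-naive children and [2, 252] for rollovers.
- Vital signs: not reached. SAP 8.4.4 plans only by-visit values and changes.
- QTcF and LFT threshold tables: reached, because they are keyed to the TE period.
- Maximum and minimum on-treatment values (SAP 8.1): unclear, because the SAP never defines on-treatment.

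**3. Scheduled records per completer in the TE period**

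- IVA-naive ECG: Day 1; Weeks 4, 12, 24, 36, 48, 60, 72, 84 and 96; Safety Follow-up = 1 + 9 + 1 = 11.
- Gap Transition ECG: Day 1; Weeks 24, 48, 72 and 96; Weeks 12, 36, 60 and 84, restored by the administrative letter in SAP 2.1; Safety Follow-up = 1 + 8 + 1 = 10.
- IVA-naive LFT with a Day 1 draw: Day 1; Weeks 2, 4, 8, 12, 18, 24, 36, 48, 60, 72, 84 and 96; Safety Follow-up = 1 + 12 + 1 = 14.

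**4. Chance that Day 1 is the maximum**

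Assume the n records are exchangeable with no drug effect. Then P(Day 1 is the maximum) = 1/n.

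- IVA-naive ECG: 1/11 = 9.1%. A simulation with within-child correlation of 0.3 or 0.6 gave 9.2% in both cases.
- Gap Transition ECG: 1/10 = 10%.
- IVA-naive LFT: 1/14 = 7.1%.
- Early discontinuation with 5 or 4 ECGs in all: 20% or 25%. With only 2 or 1 postdose ECGs: 1/3 = 33% or 1/2 = 50%.

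**5. Chance that a threshold count changes**

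Being the maximum is not enough: Day 1 must cross the threshold and no later record may. Let p be the chance that one record crosses and k the number of postdose records. With independent records the extra share of children is p(1 − p)^k. The documents give no value for p, so 1%, 2% and 5% are assumed, with k = 10 (IVA-naive ECG).

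| p | Flagged without Day 1 | Flagged with Day 1 | Extra children if all 75 were IVA-naive completers |
|---|---|---|---|
| 1% | 9.6% | 10.5% | 0.7 |
| 2% | 18.3% | 19.9% | 1.2 |
| 5% | 40.1% | 43.1% | 2.2 |

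Correlation within a child shrinks this. At p = 2%, the simulated shares were 14.7% and 15.8% at correlation 0.3 (75 × 0.0107 = 0.8 child), and 10.5% and 11.1% at 0.6 (75 × 0.0057 = 0.4 child). Whatever the correlation or number of visits, the extra share cannot exceed p, the chance that Day 1 itself crosses: 75 × 0.01 = 0.75, 75 × 0.02 = 1.5 and 75 × 0.05 = 3.75 children.

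**6. After the fix**

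An IVA-naive completer has 10 scheduled ECGs and 13 LFT records in these tables, and Day 1 cannot be the tabulated worst value.

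**The case against.** The strongest reply is that the worst-record rule sits among the visit-window rules and concerns several measurements within one window. Postbaseline windows open on day 2, so on that reading threshold analysis never sees Day 1. Ordinary usage supports this, since a predose ECG in an IVA-naive child is not on-treatment, and Protocol 12.3.4.3 asks for on-treatment QTcF extremes. The reading is possible, but the SAP does not state it. SAP 8.4.2 and 8.4.3 name the TE period and not the windows. The two are not the same set either: the TE period runs to the Safety Follow-up Visit, which SAP 8.1 generally keeps as a nominal visit outside the windows.

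Eligibility also limits the LFT side. Protocol 8.2.2 excludes abnormal liver function at screening and a history of clinically relevant AST, ALT or bilirubin above 2 × ULN. Protocol 8.1.1 requires Gap Transition children to have baseline labs without clinically significant abnormalities. Many children need no Day 1 draw, since one up to 9 days earlier can serve. All of this stands and makes a high Day 1 transaminase unlikely. It does not cover QTcF, for which Protocol 8.2 lists no criterion.

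Finally, all safety data are listed by subject (SAP 8.4), so a Day 1 value can be traced. That helps a careful reader but does not correct the table.

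**Conclusion.** The point holds as a minor correction to a stated rule. As written, the TE definition admits Day 1 predose records to the QTcF and LFT threshold tables, and nothing removes them. The likely distortion is around one child or fewer at assumed crossing rates of 1% to 2% per record, and about two at 5%, if all 75 were IVA-naive completers. The documents do not give the IVA-naive, Gap and Same-day numbers. Exchangeability over roughly two years of infant growth is a convenience for sizing, not a claim about the data.

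A reader might infer more than the documents support:

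- That all safety summaries, including vital signs, are contaminated. The day-2 windows protect the by-visit summaries, and vital signs have no threshold table.
- That every Day 1 record is pre-drug. For Same-day Transition children it is an on-drug Study 124 record; the issue there is that a parent-study value is counted in Study 126.
- That the SAP breaks a protocol rule for ECGs and labs. The protocol text that cuts at dosing, under which pretreatment events "are defined as AEs that were reported or worsened after signing the ICF up to the start of study drug dosing", defines adverse events only.
- That 9% to 10% of children would be misclassified. That is the chance that Day 1 is the maximum; far fewer would change category.

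**What to change.** Add to SAP 8.1 that the QTcF and LFT threshold tables and the maximum and minimum on-treatment values use only records collected after the first Study 126 dose, judged by date and time. Where the time is missing, exclude records scheduled predose on Day 1, which agrees with the day-2 windows in Appendix B. State that a record used as baseline is never counted as treatment-emergent, and define on-treatment in the same place. Keep the date-level rule for adverse events.

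The cost is a sentence or two in the SAP and one condition in the programs. No new data are needed: Protocol 9.4 already has the time of the Day 1 dose recorded, and the missing-time rule covers assessments without a clock time.

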**Source of Subjects Enrolled in the Observational Arm**

- Subjects who completed ivacaftor treatment in Study 124 Part B and elected not to enroll in the ivacaftor arm of Study 126
- Subjects who received at least 1 dose of ivacaftor and prematurely discontinued ivacaftor treatment in Study 124 Part B

[figure not shown]
**Investigational Drug** Active substance: ivacaftor  
Activity: CFTR potentiator  
Strength and route of administration: 25 mg, 50 mg, 75 mg, and others (to be determined based on safety and PK data from Study 124, age, and weight); granules for oral administration

**Study Duration** **Ivacaftor Arm:** Subjects will participate for approximately 128 weeks (from Day 1 through the Follow-up OE).

**Observational Arm:** Subjects will participate for approximately 96 weeks (from Day 1 through the Week 96 Follow-up Telephone Contact).

**Study Design** This is a Phase 3, 2-arm, multicenter study with an open-label ivacaftor arm and an observational arm. The study design is shown in [Figure 2-1](#).

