### **13.1.1.3 Documentation of Adverse Events**

All AEs will be collected from the time ICF is signed until the following time points:

- For subjects who do not enroll: until time of screen failure (e.g., screen failure, withdrawal of consent)
- For enrolled subjects who have a Safety Follow-up Visit: through the Safety Follow-up Visit, with the exception of ocular adverse events noted during the Follow-up OE
- For enrolled subjects who do not have a Safety Follow-up Visit: the earliest of 4 weeks  $\pm$  7 days after the last dose of study drug, or the ETT Visit, if that visit is 3 weeks or later following the last dose of study drug (see Section 9.1.1.5)

All subjects will be queried, using nonleading questions, about the occurrence of AEs at each study visit. When possible, a constellation of signs and/or symptoms will be identified as 1 overall event or diagnosis. All AEs for enrolled subjects will be recorded in the CRF and source document. AEs for subjects who are screened but not subsequently enrolled in the study will be recorded only in the subject's source documents. The following data will be documented for each AE:

- Description of the event
- Classification of "serious" or "nonserious"
- Date of first occurrence and date of resolution (if applicable)
- Severity
- Causal relationship to study drug(s)
- Action taken
- Outcome
- Concomitant medication or other treatment given

For the purposes of study analysis, if the event has not resolved at the end of the study reporting period (the Safety Follow-up Visit), it will be documented as ongoing. For purposes of regulatory safety monitoring, the investigator is required to follow the adverse event to symptom resolution or until the condition stabilizes.

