8.4.1 Adverse Events

AEs will be classified as pretreatment AEs, TEAEs, or post-treatment AEs, defined as follows:

Pretreatment AE: any AE that started before the first dose date of study drug in Study 126

TEAE: any AE that worsened (either in severity or seriousness) or that was newly developed at or after the first dose date of study drug through the end of the TE period in the current study.

Post-treatment AE: any AE that worsened (either in severity or seriousness) or that was newly developed beyond the TE period

For AEs with completely missing or partially missing start dates, if there is no clear evidence that the AEs started before or after study treatment, the AEs will be classified as TEAEs.

Details for imputing missing or partial start dates of AEs are described in [Appendix D](#).

AE summary tables will be presented for TEAEs only and will include the following:

- All TEAEs
- TEAEs by strongest relationship
- TEAEs by maximum severity
- TEAEs leading to treatment discontinuation.
- Serious TEAEs
- Related (defined as missing, possibly related, or related) TEAEs
- Serious Related TEAEs

Summaries will be presented by MedDRA System Organ Class and Preferred Term using frequency counts and percentages (i.e., number and percentage of subjects with an event). When summarizing the number and percentage of subjects with an event, subjects with multiple occurrences of the same AE or a continuing AE will be counted once. Only the maximum severity level will be presented in the severity summaries, and the strongest relationship level will be presented in the relationship summaries.

In addition, a listing containing individual subject AE data for TEAEs leading to treatment interruption, TEAEs leading to discontinuation, SAEs, and deaths will be provided separately. All AEs, including pre- and post-treatment AEs, will be presented in an individual subject data listing.

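### The SAP ends the treatment-emergent period about 4 weeks after last dose, so ocular AEs first arising at the Follow-up OE are listed but enter no AE table, and SAP 2.1 does not declare the narrower window

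*SAP*

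**What the plan says.** **SAP.** Section 8.1 runs the TE period from first dose "to the Safety Follow-up Visit, or the last dose date + 28 days for subjects who do not have a Safety Follow-up Visit" and makes it the default for safety analyses. Section 8.4.1 bounds TEAEs by that period and classes anything that starts or worsens later as a post-treatment AE. It then states that "AE summary tables will be presented for TEAEs only". Post-treatment AEs go into the listing of all AEs, and SAEs and deaths also have their own listing.

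**Protocol.** Section 12.3.4.1 defines TEAEs twice. The first definition covers events starting or increasing in severity "on or after the first dose of ivacaftor through the end of participation (as applicable) in this study". The second says that TEAEs "are defined as AEs that were reported or worsened on or after the start of study drug dosing through the the end of participation", again with the as-applicable qualifier. The same section says "Only TEAEs will be summarized in tables". The synopsis, under Study Duration, describes ivacaftor-arm participation as "from Day 1 through the Follow-up OE". Section 13.1.1.3 collects AEs in subjects who have a Safety Follow-up Visit "through the Safety Follow-up Visit, with the exception of ocular adverse events noted during the Follow-up OE". The schedules of assessments in both documents likewise keep ocular AEs, and no others, in the Follow-up OE column.

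Two protocol statements point the other way. Section 12.3.4.1 also says "All AEs through the Safety Follow-up Visit will be listed in an individual subject data listing", and 13.1.1.3, speaking of study analysis, identifies the end of the reporting period with the Safety Follow-up Visit.

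**The concern.** Safety is the primary objective. Protocol 9.2.3 explains that OEs are in the study because lens opacities were seen in juvenile rats. Ocular AEs are the one AE type still collected at the last examination, some five months off drug. Under the protocol's TEAE wording, an ocular AE arising there would count as treatment-emergent and be tabulated. Under the SAP it cannot be.

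A reader who sets the final AE tables against the protocol definition would expect them to reach the Follow-up OE. SAP 2.1 records other departures, down to an endpoint name and a dose-determination footnote, and it discusses the Follow-up OE at length. It says nothing about the TEAE window.

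**Working it through.** The plan gives no figure to reproduce here, since the study is descriptive and unpowered. The check is day arithmetic from last dose, followed by a comparison of which outputs can hold a late ocular event.

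**Timing (protocol synopsis, ivacaftor arm overview)**
- Safety Follow-up Visit: 4 × 7 ± 7 = day 21 to 35.
- TE end without that visit (SAP 8.1): day 28.
- Follow-up OE: 24 × 7 = 168, to 168 + 14 = 182.
- Smallest gap: 168 − 35 = 133 days. Largest: 182 − 21 = 161 days.
- Under the day-28 rule: 168 − 28 = 140 to 182 − 28 = 154 days.
- If the ±14-day OE allowance in the schedule footnotes were applied as well: 168 − 14 = 154, and 154 − 35 = 119 days, still outside.
- Share of the time from last dose to Follow-up OE that lies outside the TE period: 133/168 = 79% up to 161/182 = 88%.

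No in-window combination places an event dated to the Follow-up OE inside the TE period.

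**Where a late ocular event can appear**

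| Output | Starts at Follow-up OE |
|---|---|
| AE tables (SAP 8.4.1) | No |
| Listing of all AEs (8.4.1) | Yes |
| SAE and death listing (8.4.1) | If it qualifies |
| Cataract/lens-opacity incidence (8.4.6) | Lens findings only, and only the finding |
| Red reflex (8.4.6) | Listed, not summarized |

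The 8.4.6 row rests on Appendix B, which gives the ophthalmologic exam a nominal 24-Week Follow-up OE row in both Tables 11-4 and 11-5. Sections 8.4.2 to 8.4.4 restrict laboratory, ECG and vital-sign summaries to treatment-emergent measurements. Section 8.4.6 carries no such restriction, but it does not expressly set aside the TE default of 8.1 either.

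For an event that began in the TE period and worsened at the Follow-up OE, the worsening is post-treatment under 8.4.1. The severity table would then rest on what was recorded earlier. How such a worsening is entered on the CRF is not stated.

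**Illustration, on assumed counts.** The documents give neither the number of such events nor the number of subjects with a Follow-up OE. Assume one event. The 75 is planned enrolment (SAP 6.2); 50 and 25 are assumed. Intervals are Clopper-Pearson.

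| Subjects with Follow-up OE | Incidence | Exact 95% CI | Count in SAP AE tables |
|---|---|---|---|
| 75 | 1/75 = 1.3% | 0.03 to 7.2% | 0 |
| 50 | 1/50 = 2.0% | 0.05 to 10.6% | 0 |
| 25 | 1/25 = 4.0% | 0.1 to 20.4% | 0 |

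The table also shows why the denominator matters. One event over all 75 is 1.3%, a third of the 4.0% if only 25 were examined (1.33/4.00 = 0.33).

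**The case against.** The strongest reply is that the SAP resolves an ambiguity rather than departing from the protocol. Both TEAE definitions carry the as-applicable qualifier. Section 12.3.4.1, unlike the laboratory, ECG, vital-sign and physical-examination sections, is not limited to the ivacaftor arm, so the end-of-participation wording may be meant to cover the observational arm too, which enrolled no one. The listing sentence in 12.3.4.1 and the analysis sentence in 13.1.1.3 both stop at the Safety Follow-up Visit, where the SAP stops. This stands in part: a reader might infer that the SAP contradicts a clear protocol rule, and the protocol is not uniform enough to support that. But both definitions still run to the end of participation, and 13.1.1.3 expressly carves out ocular AEs at the Follow-up OE. An ambiguity resolved one way is still worth declaring.

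A reader might also infer that these events are lost or concealed. The documents do not support that. SAP 8.4.1 openly defines post-treatment AEs, says the tables exclude them and says they are listed. In a single-arm study of about 75 subjects a listing shows each case.

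Nor should a reader infer that late lens opacities escape every summary. The nominal Follow-up OE rows in Appendix B would have little purpose if that visit were left out of the 8.4.6 summary.

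Two further limits are fair. Subjects moving to commercial ivacaftor may have no Follow-up OE (SAP 2.1; protocol Table 3-3 footnote b), which shrinks the affected group by an unknown amount. And events with missing or partial start dates can be classed as TEAEs (SAP 8.4.1, Appendix D), so some late findings of uncertain onset could still reach the tables.

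**Conclusion.** The point holds in a limited form. As written, the SAP keeps every ocular AE with a recorded onset after the TE period out of the AE tables. That includes any dated to an on-schedule Follow-up OE, which falls 133 to 161 days too late. The narrower window is not declared in SAP 2.1.

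The gap has two parts: the tabulated severity, relationship and seriousness of late ocular AEs, and any table for late ocular AEs other than cataract or lens opacity. Lens-opacity incidence should be covered by 8.4.6, although that section does not say so outright.

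This rests on visits falling in window, on recorded onset dates, and on reading the end of ivacaftor-arm participation as the Follow-up OE, as the synopsis has it. The number of affected events is unknown, and the incidence figures above only illustrate assumed counts. A roughly 4-week TE period is itself a reasonable choice. The shortfall is in what is tabulated beyond it and in the missing declaration.

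**What to change.** Keep the TE period as it is, and make three changes to the SAP:

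1. **Section 8.4.1:** add one summary table of post-treatment ocular AEs by preferred term, severity, relationship and seriousness, with subjects who had a Follow-up OE as the denominator.
2. **Section 2.1:** declare that the TEAE window is narrower than the definitions in protocol 12.3.4.1.
3. **Section 8.4.6:** state that cataract/lens-opacity incidence includes the Follow-up OE.

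The cost is one table and a few sentences, with no new data. The downside is a denominator smaller than the Safety Set, and so less precise estimates. Only the declaration closes the difference between the documents; the table goes beyond the protocol's own list of outputs, but it restores what the TEAE definitions there would have tabulated.
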